- ⊕ At the end of each month, the facilitator will check the *Student Identification Form* to identify any students that have utilized the school based health center during that month.
 - If a student has used the health center, then the facilitator will record pertinent information on the *Health Center Participation Form* that is on the password protected excel document for the monthly time period in review.
- ⊕ At the end of each month, the facilitator will meet with a member of the play2PREVENT team for approximately 10-15 minutes. During this brief meeting the SBHC facilitator and the play2PREVENT team member will print the *Health Center Participation Form* for the time period at hand and both parties will sign-off on its completeness. The printed sheet will then be placed in the secured lockbox with the USB drive.
- ⊕ Use the 3000z billing code for participants that come in for a STI/HIV test to protect privacy during insurance billing.

Data analysis

Phase 2: Data analyses general considerations: All statistical analyses will be conducted based on the “intent-to-treat” principle, through the use of either SPSS or SAS statistical packages.

Statistical analyses: **Primary outcome:** The primary outcome will be the proportion of participants who engage in HTC within the six-month study period. Rates of HTC among intervention and control participants at six months will be compared using Fisher’s exact test and a 2-sided test at the 0.05 level. **Secondary outcomes:** To address the secondary outcomes we will use repeated measures ANCOVAs (with Bonferroni corrections to account for multiple statistical tests). The models will include attitudes, perceived barriers, perceived norms, intentions, self-efficacy, and knowledge as dependent variables, with study condition as the independent variable, and sex, ethnicity, and history of testing as covariates. **Mediators and moderators:** Data will be collected on potential mediators and moderators and examined using conventional methods¹¹³. Baseline levels of these mediators and moderators will be used in the models to assess whether these variables affect the primary or secondary outcomes. In addition, because these variables might change over time during participation in the study, they will also be considered as time-varying covariates. **Mediators:** Based on our logic model¹¹² that will guide the development of the proposed intervention, we predict that 1) attitudes, 2) perceived barriers, 3)

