perceived norms, 4) intentions, 5) self-efficacy, and 6) knowledge will mediate the effects of the intervention on HTC at 6 months. The selection of mediators is based upon the logic model and given the proposed game will have many different components (as our current **PlayForward** game does), and given our experience of including all of these components into a game intervention, this selection of mediators was carefully guided by the process of constructing the logic model. We will use the criteria proposed by Baron and Kenny (1986)¹¹³ to test the relationships among the outcomes and presumed mediators. According to these criteria, four conditions should be met to establish mediation. We outline these conditions using our specific hypothesis that intentions mediate the relationship between the study condition (intervention or control) and HTC as an example. The first condition is that the study condition is directly related to HTC. Second, the intervention condition has a direct effect on the mediator (intentions). Third, intentions have a direct effect on HTC, when the study condition is controlled. Fourth, if intentions mediate the intervention condition-HTC relationship, the direct effect of the study condition on HTC is reduced or eliminated after controlling for intentions. To test the significance of mediation effect, which is called indirect effect, we will calculate Sobel's test¹¹⁴⁻¹¹⁶ for each proposed mediator. Sobel's test determines the significance of the mediation effect by testing the null hypothesis that the indirect effect coefficient is zero (i.e. whether the indirect effect of the independent variable on the dependent variables is significantly different from zero). **Moderators:** Variables that predict the outcome variable (first substance use) differently between treatments will be considered to be moderators using the model outlined by Kraemer et al¹¹⁷. In order to be considered a moderator, the variable must be present prior to randomization and must not be related to the independent variable (**PlayTest!** vs. control games). Pre-randomization variables that interact with the independent variable in predicting the outcome variable (HTC) will be considered moderators of treatment. Variables that predict the outcome variable but do not significantly interact with treatment condition will be classified as nonspecific pre-randomization predictors.

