Statistical analyses: **Primary outcome:** Due to COVID-19’s impact on this study’s initial primary outcome of the number of participants that were tested for HIV at the 6 month timepoint, the primary outcome has been modified. Behavioral outcomes are influenced by attitudes and intentions; therefore, we will explore attitudes and intentions in our study, with **attitudes about around HTC** as the new primary outcome. After a thorough review of existing literature, the team decided that the primary outcome would be changed to measuring participant’s attitudes around HTC at 6 months for the full cohort, with intentions and behaviors being assessed as secondary outcomes. **Secondary outcomes:** To address the secondary outcomes we will use repeated measures ANCOVAs (with Bonferroni corrections to account for multiple statistical tests). The models will include attitudes, perceived barriers, perceived norms, intentions, self-efficacy, and knowledge as dependent variables, with study condition as the independent variable, and sex, ethnicity, and history of testing as covariates. **Mediators and moderators:** Data will be collected on potential mediators and moderators and examined using conventional methods¹¹³. Baseline levels of these mediators and moderators will be used in the models to assess whether these variables affect the primary or secondary outcomes. In addition, because these variables might change over time during participation in the study, they will also be considered as time-varying covariates. **Mediators:** Based on our logic model¹² that will guide the development of the proposed intervention, we predict that 1) attitudes, 2) perceived barriers, 3) perceived norms, 4) intentions, 5) self-efficacy, and 6) knowledge will mediate the effects of the intervention on HTC at 6 months. The selection of mediators is based upon the logic model and given the proposed game will have many different components (as our current *PlayForward* game does), and given our experience of including all of these components into a game intervention, this selection of mediators was carefully guided by the process of constructing the logic model. We will use the criteria proposed by Baron and Kenny (1986)¹¹³ to test the relationships among the outcomes and presumed mediators. According to these criteria, four conditions should be met to establish mediation. We outline these conditions using our specific hypothesis that intentions mediate the relationship between the study condition (intervention or control) and HTC as an example. The first condition is that the study condition is directly related to HTC. Second, the intervention condition has a direct effect on the mediator (intentions). Third, intentions have a direct effect on HTC, when the study condition is controlled. Fourth, if intentions mediate the intervention condition-HTC relationship, the direct effect of the study condition on HTC is reduced or eliminated after controlling for intentions. To test the significance of mediation effect, which is called indirect effect, we will calculate Sobel's test¹¹⁴⁻¹¹⁶ for each proposed mediator. Sobel's test determines the significance of the mediation effect by testing the null hypothesis that the indirect effect coefficient is zero (i.e. whether the indirect effect of the independent variable on the dependent variables is significantly different from zero). **Moderators:** Variables that predict the outcome variable (first substance use) differently between treatments will be considered to be moderators using the model outlined by Kraemer et al¹¹⁷. In order to be considered a moderator, the variable must be present prior to randomization and must not be related to the independent variable (*PlayTest!* vs. control games). Pre-randomization variables that interact with the independent variable in predicting the outcome variable (HTC) will be considered moderators of treatment. Variables that predict the outcome variable but do not significantly interact with treatment condition will be classified as nonspecific pre-randomization predictors.

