
Collection and analysis of the in-game data: We will build on systems we have developed to analyze the data collected by the game software or the in-game data⁹⁸, which will serve as the foundation for analytics system built into the game. Briefly, using Player Game State Data (the traditional save/load data so a player can save their progress and pick up later where they left off) and Activity Logging Data (the relevant time-stamped player

actions during gameplay), we will examine the paths taken and decisions made by each player, documenting their exposure to content and the “learning curve” from the in-game data.

All data collected from the assessments will be entered directly into the secure web-based system, OnCore, Yale’s enterprise-wide clinical research management system. OnCore is a fully integrated system development by Forte, which includes three modules: 1) Clinical research management (CRM); 2) Bio-specimen management (BSM); and 3) Patient registry. This project will utilize the CRM module as the electronic data capture system for all case report form data and to support subject tracking. Data will be entered into the OnCore system either by research staff, or with the more sensitive assessments, by the participant themselves. This method limits data entry-associated errors. Before enrolling participants into the intervention, we will conduct a pilot test with two to three participants to assess acceptability and usability of the game, make changes as needed, and confirm data collection procedures.

New proposed plan for analysis approach due to COVID-19

1. Revise power calculations to ensure that a clinically meaningful effect size for the new primary outcome (attitudes around HTC at 6 months in the full cohort) can be detected.
2. Examine **attitudes** around HTC as primary outcome at 6 months in the full cohort.
3. Examine **intentions** to get tested at 6 months in full cohort.
4. Examine **HTC** at 6 months in smaller cohort of students that were able to reach the full 6 months of the study without being impacted by the pandemic (N=135). This study is not powered to detect a difference at this smaller sample size.

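### Sobel's test is a conservative choice for mediation of 6-month HTC at the sizes available, and the plan does not say whether a failed causal-steps condition overrides it

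*Combined protocol and SAP*

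**What the plan says.** The mediation text appears in Section 4 (Research Plan, Data analysis) and again in Section 13 (Statistical Considerations). It predicts that attitudes, perceived barriers, perceived norms, intentions, self-efficacy and knowledge "will mediate the effects of the intervention on HTC at 6 months".

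It adopts the Baron and Kenny criteria, under which "four conditions should be met to establish mediation". Taking intentions as the example, it begins: "The first condition is that the study condition is directly related to HTC". The other three conditions are that arm affects the mediator, that the mediator affects HTC given arm, and that the arm effect shrinks once the mediator is in the model.

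It then says: "To test the significance of mediation effect, which is called indirect effect, we will calculate Sobel's test", and this is to be done "for each proposed mediator". No condition is attached to that calculation. No bootstrap or product-distribution method is named, and neither a cohort nor a significance level is given for mediation.

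Three other statements matter:

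- Section 13 already provides that "Baseline levels of these mediators and moderators will be used in the models".
- The only arm-HTC test specified is in Section 4, under the pre-COVID primary outcome: Fisher's "exact test and a 2-sided test at the 0.05 level".
- The COVID-19 analysis plan (item 4) keeps 6-month HTC only for the 135 students not affected by the pandemic, and says: "This study is not powered to detect a difference at this smaller sample size".

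**The concern.** Sobel's test refers the estimated indirect effect, divided by its standard error, to a normal distribution. A product of two estimates is skewed unless at least one path is very precisely estimated, so in a small sample the test rejects too rarely. Real mediation can then be missed although the data would support it under a better-matched interval.

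The second issue is an open rule. The text makes the four conditions the criterion for establishing mediation, yet calculates Sobel's test for every mediator. If a failed first condition overrides a significant Sobel result, mediation cannot be established more often than the arm-HTC comparison succeeds, however strong the mediator. If it does not, only the conservatism remains. The analyst should not have to choose after seeing the results.

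At stake is the plan's check on whether the game affects testing through its logic-model variables. No primary conclusion depends on it.

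**Working it through.** **The plan's own figures.** No power or sample size is stated for mediation, so there is none to reproduce. For scale, the HTC sample size is 118 per group at 85% power and two-sided 0.05. With h the difference in arcsine-transformed proportions, this implies h = (1.960 + 1.036)/√(118/2) = 2.996/7.681 = 0.39. The stated effect size of 0.27 carries no metric, so both values are used below. The dropout step reproduces: 118/0.8 = 147.5, rounded up to 148 per group, 296 in total.

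**What a binding first condition would cap.** With 68 and 67 per arm, √(68×67/135) = 5.81, and power = Φ(5.81h − 1.96):

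- h=0.27: Φ(−0.39) = 35%
- h=0.39: Φ(0.31) = 62%
- h=0.54 (a larger assumed effect): Φ(1.18) = 88%

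Simulated with Fisher's test, these become 27-30%, 53-58% and 84-86%.

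**Why Sobel's test loses power.** Let za and zb be the z-statistics of the arm-mediator and mediator-HTC paths. Sobel's statistic is za·zb/√(za² + zb²). The product interval excludes 0 when P = Φ(−za)Φ(zb) + Φ(za)Φ(−zb) is below 0.025 or above 0.975. Illustration with za = zb = 2.5:

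- Sobel: 6.25/3.536 = 1.77, two-sided p = 0.077, not significant.
- Product: P = 2 × 0.0062 × 0.9938 = 0.0123, so the interval excludes 0.

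**Simulation.** The documents give no HTC rates or path sizes. Assumed: control HTC 10% or 20%; mediator shift 0.4 or 0.6 SD; odds ratio 2 per SD; mediator = shift × arm + 0.5 × baseline + residual with SD 1; logistic HTC on mediator and arm; N=135; 4,000 replicates. The sequence column requires Fisher p<0.05, both paths p<0.05, a reduced arm coefficient and Sobel p<0.05. Cells show percent detected, in the order control HTC/shift = 10%/0.4, 10%/0.6, 20%/0.4, 20%/0.6, without baseline adjustment.

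| Total arm effect | Full sequence | Sobel alone | Product interval | Product minus Sobel |
|---|---|---|---|---|
| Full mediation (h=0.08-0.16) | 1.0, 3.7, 3.2, 9.0 | 17.3, 42.9, 32.6, 66.1 | 37.3, 61.0, 53.4, 82.2 | 20.0, 18.1, 20.8, 16.1 |
| h=0.27 | 7.4, 14.2, 13.6, 21.6 | 21.2, 49.1, 34.3, 68.3 | 43.8, 68.6, 54.9, 84.2 | 22.6, 19.5, 20.6, 15.9 |
| h=0.39 | 16.4, 30.8, 22.5, 42.6 | 25.1, 52.7, 34.5, 69.8 | 46.6, 72.9, 55.4, 85.0 | 21.5, 20.2, 20.9, 15.2 |
| h=0.54 | 24.7, 51.0, 33.9, 61.9 | 27.8, 59.4, 37.9, 71.1 | 50.3, 77.4, 58.2, 86.2 | 22.5, 18.0, 20.3, 15.1 |

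Like for like, the gain over Sobel's test is 15-23 points. With baseline adjustment on both sides (h up to 0.39), Sobel's test detects 18-67% and the product interval 37-79%. The further loss if the conditions override, Sobel minus sequence, is 9-57 points up to h=0.39 and 3-9 points at h=0.54.

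**Other settings.** A second set of 48 scenarios (N=135, 237 and 296; control HTC 10% or 25%; shift 0.27-0.5 SD; 0.5 or 0.8 log-odds per SD) gave a gain over Sobel's test of 0.5-22.7 points, smallest with large paths and N=296.

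**False positives per mediator, no confounding.** Full sequence 0-1%, Sobel 0-3%, baseline-adjusted product interval 0-5%, percentile bootstrap 4-7%.

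**False positives with confounding.** Assumed: an unmeasured confounder correlated 0.5-0.7 with the mediator residual, odds ratio 2 for HTC, a shifted mediator, and no effect of mediator or arm on HTC. At N=135, false mediation was declared in 0-1% (unadjusted full sequence), 2-25% (unadjusted Sobel) and 11-54% (baseline-adjusted product interval).

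**The case against.** Four objections have weight.

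- **This is a preference about efficiency, not an error.** The plan names a cited method and a test, and discloses that the 6-month HTC cohort is unpowered. That stands, and it limits the severity. Sobel's test is conservative, not invalid.
- **The largest losses depend on one reading.** A reader might infer that failing the first condition stops or voids Sobel's test, and so charge the plan with the 9-57 point loss. The documents do not support that: the calculation is stated for every mediator without a condition. Equally, nothing says that a significant Sobel result suffices when a condition fails. Only the 15-23 points apply on either reading of how Sobel's test is used. The largest gate losses also arise where the total effect is h=0.08-0.16, far below the 0.39 implied by the design.
- **The baseline-adjusted interval does not always beat unadjusted Sobel.** At N=237, with the same rates assumed at 3 months, the ranges under full mediation are 57-97% (unadjusted Sobel) and 73-95% (adjusted interval), so there is no gain at the top. This stands; the claim holds like for like.
- **The first condition gives some protection.** When the arm has no effect on HTC, requiring an arm-HTC relation nearly eliminates false mediation caused by confounding. This stands. Reporting regardless of that condition is a trade-off, which is why the causal-steps results should stay in the report.

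**Conclusion.** The concern holds in a limited form. Sobel's test is a conservative choice for the six planned indirect effects, and the plan leaves open whether a failed condition overrides it. Under the assumed values, a product-distribution interval gains about 15-23 points at N=135, and less at N=237 or with larger paths. The direction was the same in every like-for-like scenario of true mediation tried; the size depends on rates and paths that the documents do not give.

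Two inferences are involved: that N=135 is the relevant cohort, and that Fisher's test would be the check of the first condition. A reader might also infer that the replacement is a clean 5% test or that it would establish causal mediation. Neither follows, because randomisation does not remove mediator-outcome confounding. Severity is minor: the analysis is ancillary and HTC is no longer the primary outcome.

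**What to change.** In the mediation text of Sections 4 and 13:

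1. Replace Sobel's test with a 95% product-distribution confidence interval for each of the six indirect effects, using the baseline mediator level that the plan already includes. A percentile bootstrap is an alternative, slightly liberal in these checks.
2. State that the interval is reported whether or not the first condition is met, with the arm effect on HTC and the causal-steps results alongside.
3. Label all six results exploratory and non-causal, and name mediator-outcome confounding as the reason.

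The cost is a wording change and a short script on data already planned. The statistical price is a rise in false positives per mediator from 0-3% to about 5% without confounding, and well above that with it. Power also stays modest at N=135: 11-50% if the six intervals are corrected for multiplicity (odds ratio 2, h up to 0.39).

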Adequacy of sample size: A sample size calculation was done using the G*Power software. An effect size of 0.27, was estimated (conservatively) based on previous research¹⁰³. With equal numbers of subjects in each group, and alpha = 0.05, to provide 85% power to detect a difference in HTC rates at six months controlling for history of testing, sex, and ethnicity, a sample of 118 per group (total N = 236) is required. Based on adherence rates from our test of the original ***PlayForward*** game we assume 80% retention at 6 months. To account for the 20% dropout we will seek to enroll 296 participants.

Randomization: We will use a stratified randomization procedure¹⁰⁴ to assign participants to one of the study arms. Gender, race/ethnicity, and age will be included in the randomization algorithm because these variables have been found to be important predictors of HTC in adolescents¹⁰³. The stratification would be as follows two gender groups (girl vs. boy), two ethnic groups (Hispanic vs. non-Hispanic), three groups for race (White, African-American, Other) and two groups for age – (14, 15, 16 vs. 17 and 18). A block size of 6 will be used for the stratification process.

Treatment conditions: The research staff will orient the participants to the use of either ***PlayTest!*** or the control videogames. Players in both groups will play through an online tutorial demonstrating the mechanics of the game. Each player will use a dedicated device to access their game on the web and a set of headphones that they will use during each gameplay session. The research staff will oversee all gameplay to ensure that participants are playing and to field any questions. The control videogames (**see below**) will be engaging and fun but will be devoid of relevant content.

Assessments: We will assess participant characteristics (demographic), outcomes, and process measures (Table 1). For outcomes, we will collect data on actual HTC and assess a variety of mediators and moderators among teens (e.g., attitudes, intentions, knowledge). To measure actual testing in our participants, we will work with health care professionals at school clinics located on the premises of our partner sites to determine if students who participated in our study subsequently got tested. This data will be collected based on the protocol of the specific clinic, and the participants’ personal health information will be de-identified (including results) before being

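### The moderator rule classifies a baseline variable as nonspecific because its interaction with arm is not significant, in a trial with little power for interactions

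*Combined protocol and SAP*

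**What the plan says.** The moderator paragraph appears in the same words in section 4 (Research Plan, Data analysis) and section 13 (Statistical Considerations, Phase II).

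- **Positive side of the rule:** "Pre-randomization variables that interact with the independent variable in predicting the outcome variable (HTC) will be considered moderators of treatment".
- **Negative side:** "Variables that predict the outcome variable but do not significantly interact with treatment condition will be classified as nonspecific pre-randomization predictors".
- **Candidates:** the introduction to the paragraph says only this: "Data will be collected on potential mediators and moderators and examined using conventional methods". No list or number of moderators is given, and no significance level for the interaction tests.
- **Multiplicity:** the only Phase II adjustment belongs to another analysis: "To address the secondary outcomes we will use repeated measures ANCOVAs (with Bonferroni corrections to account for multiple statistical tests"). The sentences on adjusting alpha when needed, and on the analyses being exploratory, belong to the Phase I plan.
- **Sample:** section 4 sizes the trial at 118 per group (236 evaluable), with "alpha = 0.05, to provide 85% power to detect a difference in HTC rates at six months". After COVID-19, the section 13 list puts HTC at 6 months in a cohort of 135 and says: "This study is not powered to detect a difference at this smaller sample size". It adds HTC at 3 months in 237.

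The paragraph names HTC as the outcome in the classification sentence, although an earlier sentence names first substance use. The working below uses HTC.

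**The concern.** A non-significant interaction can mean that the effect is similar at both levels of the variable, or that the trial could not tell. The rule does not separate the two. It gives the variable a named class, and that class asserts something: the variable predicts testing but does not change what the game does. The only support required is a p-value above an unstated threshold; no interaction estimate or interval is asked for.

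The opposite error is also open. Each candidate tested at 0.05 adds a chance of a false moderator, and the Phase II correction does not cover these tests.

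At stake are the statements the trial will make about which adolescents the game works in. The primary comparison is not affected.

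**Working it through.** **1. The plan's own figure.** The dropout step reproduces: 118/0.8 = 147.5, so 148 per arm and 296 in total. The 118 itself cannot be verified, because the metric of the 0.27 effect size is not stated. Read as a standardised difference, 0.27 would need 247 per arm two-sided. Conversely, 118 per arm at 85% power corresponds to √(2/118) × (1.960 + 1.036) = 0.39 SD. I take the plan's 85% at N=236 as given, which favours the plan.

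**2. Power for an interaction.** Assume a two-level moderator split 50/50, a two-sided 0.05 test and a normal approximation. The plan states "a 2-sided test at the 0.05 level" for the original HTC comparison; I assume the same level for the interactions.

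- Variance of the main effect: 4σ²/N. Variance of the interaction contrast (four cells of N/4): 16σ²/N. The standard error doubles.
- Expected z for the main effect at N=236: 1.960 + 1.036 = 2.996.
- Expected z for an interaction m times the main effect: m × (2.996/2) × √(N/236). Power is Φ(that value − 1.960), plus a negligible opposite tail.

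| N | m | Expected z | Power |
|---|---|---|---|
| 236 | 1 | 1.498 | 0.32 |
| 236 | 2 | 2.996 | 0.85 |
| 135 | 1 | 1.133 | 0.205 |
| 135 | 2 | 2.266 | 0.62 |

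Power reaches 50% when the expected z is 1.960: m = 1.960/1.498 = 1.31 at N=236, and 1.960/1.133 = 1.73 at N=135. The documents give no interaction size, so m is an assumption.

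**3. What the rule does with a true moderator.** Assumed example: control 10% in both halves; game 25% in one half and 10% in the other; N=135 in four near-equal cells (34, 34, 34, 33).

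- True interaction: (0.25 − 0.10) − (0.10 − 0.10) = 0.15.
- Standard error: √(3 × 0.09/34 + 0.1875/33) = 0.117. Expected z = 1.285, and power is about 25%.

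I then simulated the full rule (200,000 runs, Wald tests at 0.05). A variable counts as predicting the outcome if its average effect over the two arms is significant.

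| Result at N=135 | Share of trials |
|---|---|
| Interaction significant: moderator | about 26% |
| Not significant, but predicts outcome: nonspecific (wrong) | about 17% |
| Neither: no label | about 57% |

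At N=237 the interaction is detected in about 41% of trials and the wrong label is given in about 20%.

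**4. False moderators.** With k independent tests at 0.05 and no true moderators, the chance of at least one is 1 − 0.95^k: 19% for k=4, 26% for k=6, 46% for k=12 and 51% for k=14. Twelve is one test for each domain measured at baseline in Table 1. Since the plan gives no number, this is an assumed range.

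**The case against.** **The miss rate is not the mislabelling rate.** A variable becomes nonspecific only if it also predicts the outcome. This stands. A reader might infer that most true moderators are mislabelled; in the example the wrong label occurs in about 17% of trials, and most misses end with no label.

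**Large interactions are found.** This stands too. Above about 1.3 times the main effect at N=236, or 1.7 times at N=135, detection is more likely than not.

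**False moderators are not shown to be likely.** Correct. The chance passes one half only at about 14 independent tests, no number is planned, and the Table 1 scales overlap, which would usually lower it. It remains a material risk without a stated control.

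**The plan follows a cited framework and never says the effect is equal.** It does not use those words. But the class is assigned on non-significance alone, with no estimate beside it, so the inference is built into the rule.

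**The plan already warns about N=135.** It does, for the HTC comparison between arms. That warning is not carried into the moderator paragraph, and N=237 improves interaction power only to about 41% in the example.

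**Two further readings fail.** One might infer that the condition that a moderator "must be present prior to randomization and must not be related to the independent variable" will discard about one variable in twenty through chance imbalance. The text reads as a definition that randomisation satisfies; no significance screen is described. One might also infer that the labels will decide who receives the game. The documents plan wide distribution and do not link it to moderator results.

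**Conclusion.** The concern holds in a limited form. The rule turns a non-significant interaction into a substantive class, and the trial cannot support that step for interactions of moderate size: power is about 32% at N=236 and 20% at N=135 when the interaction equals the detectable main effect. Following the rule can therefore produce wrong classifications, in about one trial in six in the example at N=135. The lack of error control adds a 19% to 46% chance of a false moderator over 4 to 12 independent tests.

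These figures rest on the plan's 85% power at N=236, a 50/50 two-level moderator, two-sided 0.05 tests, independence for the false-positive range, and the assumed testing rates in the example. A less even split lowers the power; a larger interaction raises it. The claims that most true moderators are mislabelled, or that false ones are more likely than not, are not supported.

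**What to change.** In the moderator paragraphs of sections 4 and 13:

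- Replace classification by interaction p-value with the arm-by-variable interaction estimate and its 95% confidence interval for each candidate.
- Name a short set in advance, for example the stratification factors and the baseline score of the outcome.
- Label the analysis exploratory.
- State that a non-significant interaction is not evidence of equal effect.

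Extending Bonferroni to these tests while keeping the classes would not be enough. With 6 candidates it would cut power at N=236 from about 32% to 13% for an interaction equal to the main effect, so more true moderators would fail the interaction test.

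The cost is wording only, with no new data or visits. Fewer variables will receive a definite label.
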